6.1.1 Screening Period

6.1.1.1 Informed Consent Form

All subjects must provide written or witnessed verbal informed consent prior to participating in any Screening evaluations or any other study activities.

The Investigator or his/her approved designee must explain the nature of the study protocol and associated risks to the potential study subject. The potential subject must be allowed sufficient time to review the information and to ask questions. The date that the informed consent form is signed, a brief description of the consent process (i.e., questions asked by the subject) and the name of the individual who obtained the consent will be recorded in the subject's source documentation. A copy of the signed informed consent form will be provided to each subject. The date and confirmation that informed consent was obtained will be recorded in the electronic case report from (eCRF).

6.1.1.2 Demographics and General Medical and Social History

Subject demographic information and medical history will be recorded at Screening Days (-45 to -4). Demographic information will include date of birth, gender, race, and ethnicity. Medical history will include medical diagnoses, major surgical procedures within the last 3 years, and social history (tobacco, drug, and alcohol use). Findings will be documented in the source documentation and eCRF.

6.1.1.3 Physical Examination

A general physical examination completed by trained staff will include at minimum an examination of general appearance, skin, eyes, ears, nose, throat, neck/thyroid, lungs, heart, upper/lower extremities, lymph nodes, abdomen, musculoskeletal system and neurological system. Additional systems will be evaluated as needed.

hysical exam findings must be recorded in the source documentation and include the date and name of the individual conducting the examination. Physical exam findings will be recorded in the eCRF.

A brief physical examination will include assessment of heart, skin, lungs, cardiovascular system, and abdomen, and extremities. Interim physical examinations will be performed at the discretion of the Investigator, if necessary, to evaluate AEs or clinical laboratory abnormalities. Height and weight will be measured, at Screening and at Day 35 ± 3 .

6.1.1.4 Height/Weight and Calculation of Body Mass Index

Height and weight will be measured at Screening and Day 35 ± 3 during the physical examination for calculation of body mass index (BMI). BMI will be calculated within the EDC system.

6.1.1.5 Standard Vital Signs

Vital signs will be measured at the time points indicated in the Schedule of Events (Appendix 3). Vital sign measurements will include SBP, DBP, body temperature, RR, and HR. The subject will have rested in a supine position for ≥ 10 minutes before all measurements are taken.

Note: Vital signs collected during the initial 60 minutes of infusion of study drug require only the SBP, DBP and HR.

The Investigator will determine whether any of the vital sign measurements are clinically significant (CS) or not clinically significant (NCS). Clinical significance is defined as any variation in results that has medical relevance and may result in an alteration in medical care (e.g., active observation, diagnostic measures, therapeutic measures). If a CS change from Screening values is noted, the CS value and reason for clinical significance will be documented on the AE page of the eCRF. The Investigator will continue to monitor the subject with additional assessments until the value has reached either the reference range or the value at Screening or until the Investigator determines follow-up is no longer medically necessary.

6.1.1.6 12 Lead Electrocardiogram

Twelve-lead ECGs will be obtained after the subject has rested in the supine position for ≥ 10 minutes at scheduled timepoints or as clinically indicated based on reported AEs or laboratory findings, as necessary.

The Investigator should review and sign the ECG for any immediate issues.

Electrocardiogram assessments will include comments concerning whether the tracings are normal or abnormal, rhythm, presence of arrhythmia or conduction defects, morphology, and any evidence of MI, or ST-segment, T-Wave, and U-Wave abnormalities. In addition, measurements of these intervals will be reported: RR interval, PR interval, QRS width, and uncorrected QT, QTcB, QTcF. The Investigator will determine whether any of the 12-lead ECG results are CS or NCS.

Clinical significance is defined as any variation in results that has medical relevance and may result in an alteration in medical care (e.g., active observation, diagnostic measures, therapeutic measures). If a CS change from Screening is noted, the CS value and reason for CS will be documented on the AE page of the eCRF. The Investigator will continue to monitor the subject with additional assessments until either the values have reached either reference range or the

values at Screening or until the Investigator determines follow-up is no longer medically necessary.

The study site will provide a calibrated ECG machine for use during the study unless otherwise provided by the Sponsor. Site personnel must assess the quality of the ECG to ensure that the test was collected appropriately and to repeat the ECG if necessary (i.e., if artifact(s) are present).

6.1.1.7 Laboratory Testing

All scheduled clinical laboratory tests will be performed by Medpace with the exception of Day -1 clinical laboratory testing which should be performed locally to provide results prior to randomization. Pharmacokinetic and immunogenicity testing will be performed by Frontage Labs, Exton, Pennsylvania. Blood will be collected at the time points indicated in the Schedule of Events (Appendix 3) and will be prepared using standard procedures defined in the laboratory manual. Repeat clinical laboratory tests of scheduled Medpace tests may be performed locally or centrally at the discretion of the Investigator, if deemed necessary, to evaluate inclusion and exclusion criteria, for urgent safety assessments, or to follow-up on clinical laboratory abnormalities. The local clinical laboratory used to perform tests must provide laboratory certification and the reference ranges for all clinical laboratory parameters.

Abnormal clinical laboratory values will be flagged as either high or low (or normal or abnormal) based on the reference ranges for each laboratory parameter. The Investigator will determine whether any of the abnormal high or low results are CS or NCS.

Clinical significance is defined as any variation in results that has medical relevance and may result in an alteration in medical care (e.g., active observation, diagnostic measures, therapeutic measures). If a CS change from the Screening value is noted, the CS value and etiology or reason for clinical significance will be documented on the AE page of the eCRF. The Investigator will continue to monitor the subject with additional assessments until the values have reached either the reference range or the values at Screening or until the Investigator determines that follow-up is no longer medically necessary.

When scheduled procedures overlap at the same time point (see Schedule of Events - Appendix 3), there must be planning to collect the specific information within the designated time window. Accordingly, the importance of these procedures are:

- 1. *Blood collection* (whether for PD, PK, immunology, or safety) should always be collected at the designated time point (if possible). However, multiple collections (PD, PK, immunology, and safety) may be required at the same time point. Therefore, the recommendation is for blood to be drawn in this order: PD, PK, immunology, and safety (see relevant lab collection manual(s) from Medpace or MLM Medical Labs for additional information related to collection of PD samples).
- 2. If time permits, *vital sign measurements* should be completed just prior to or just after blood collection; this may be still be done within the designated window in the Schedule of Events (Appendix 3).

All clinical laboratory data will be evaluated by the Investigator (Principal or physician Sub-Investigator) and clinical relevance will be assessed for abnormal values and the assessment will be documented on the laboratory report. A copy of the reports will be maintained as part of the source documentation. Additionally, a copy of the report may be included with the eCRF.

Standard rapid urine drug Screening test kits will be supplied for local testing. The test kit may check (but not limited to) for drugs such as cocaine, cannabinoids, opiates, benzodiazepines, PCPs, amphetamines, methamphetamines, barbiturates, methadone, alcohol or additional drugs not listed.

6.1.1.7.1 Serology for HIV, Hepatitis B, and Hepatitis C

All subjects will be screened for human immune deficiency virus (HIV) type I and II antigen or antibodies, hepatitis B, and hepatitis C at screening. Evaluation for HIV seropositivity will consist of enzyme-linked immunosorbent assay (ELISA) and, if positive, will be confirmed by Western blot analysis. Appropriate counseling will be made available to the subject in the event of a positive finding. Notification of state and federal authorities, as required by law, will be the responsibility of the Investigator.

6.1.1.7.2 Pregnancy Test

A blood pregnancy test result from either the local or central laboratory is required for female subjects of childbearing potential. Results must be negative in order for subjects to be randomized in the study.

6.1.1.7.3 Follicle-Stimulating Hormone (FSH) Level

Follicle stimulating hormone level may be performed at Screening using local or central laboratory, for confirmation of postmenopausal status as directed by the Investigator.

6.1.1.7.4 Lipid Profile

A lipid profile includes (total cholesterol [TC], high-density lipoprotein cholesterol [HDL-C], low-density lipoprotein-cholesterol [LDL-C], low-density lipoprotein/high-density lipoprotein (LDL/HDL) ratio, and triglycerides [TG]).

6.1.1.7.5 General Safety Laboratory Testing and Confirmation of Eligibility

Refer to laboratory manual for processing requirements. Any laboratory result including alcohol and drug test results may be repeated or performed locally for clinical follow-up as needed by Investigator.

The following clinical laboratory assessments will be performed:

Table 2 List of Clinical Laboratory Assessments

Hematology	Complete blood count (CBC) with differential
	hematocrit (hct)
	hemoglobin (Hgb)
	mean corpuscular hemoglobin (MCH)
	mean corpuscular hemoglobin concentration (MCHC)
	mean corpuscular volume (MCV)
	mean platelet volume (MPV)
	platelet count
	erythrocyte (red blood cell [RBC]) count
	total and differential leukocyte (white blood cell [WBC]) count
Serum Chemistry	alanine aminotransferase (ALT)
	albumin

	alkaline phosphatase (ALP)
	aspartate aminotransferase (AST)
	bicarbonate
	bilirubin (total and direct)
	blood urea nitrogen (BUN)
	calcium
	chloride
	cholesterol
	total
	high-density lipoprotein (HDL)
	calculated low-density lipoprotein (LDL)
	creatine phosphokinase
	creatinine
	gamma-glutamyl transferase (GGT)
	glucose
	HgbA1C
	lactate dehydrogenase (LDH)
	magnesium
	phosphorus
	potassium
	sodium
	thyroid stimulating hormone (TSH; Screening only)
	total protein
	triglycerides (repeat fasting triglyceride if TG >500)
	uric acid
Coagulation	activated partial thromboplastin time (aPTT)
Couguration	international normalized ratio (INR)
	partial thromboplastin time (PTT) *
	prothrombin time (PT) [#]
Urinalysis	
Officiallysis	appearance bilirubin
	color
	glucose
	ketones
	leukocyte esterase
	reflex microscopy (at Screening and Check-in only, if dipstick is
	positive for protein or blood value $\geq 1+$); includes
	bacteria casts
	crystals epithelial cells
	RBCs WBCs
	nitrites occult blood
	pH protein
	specific gravity (SpGr) turbidity
	urobilinogen
Sanalaan (Sanaaning anlar)	
Serology (Screening only)	hepatitis B
	hepatitis C
	human immunodeficiency virus (HIV)
	types 1 and 2 antigen or antibodies

Other analyses	stool for occult blood
2	urine drug screen may include (not limited to and may vary based
	on the testing kits provided):
	amphetamines and methamphetamines
	barbiturates
	benzodiazepines
	cannabinoids
	cocaine
	PCPs
	opiates
	methadone
	urine alcohol
	female subjects:
	follicle-stimulating hormone (FSH; Screening only)
	serum pregnancy test (human chorionic gonadotropin)

6.1.1.7.6 Calculation of Estimated Glomerular Filtration Rate

Estimated glomerular filtration rate (eGFR) will be calculated by the central laboratory from serum creatinine using the IDMS-Traceable MDRD formula and reported on the eCRF as follows.

Estimated glomerular filtration rate will be calculated by the central laboratory from serum creatinine using the IDMS-Traceable MDRD formula as follows.

Conventional units

GFR $(mL/min/1.73 \text{ m}^2) = 175 \text{ x} (S_{cr})^{-1.154} \text{ x} (Age)^{-0.203} \text{ x} (0.742 \text{ if female}) \text{ x} (1.212 \text{ if African American})$

SI units

GFR (mL/min/1.73 m²) = 175 x (S_{cr}/88.4)^{-1.154} x (Age)^{-0.203} x (0.742 if female) x (1.212 if African American)

6.1.2 Randomization

This is a double-blind placebo controlled trial. For further details on randomization please refer to section 7.2.2.

6.1.3 Active Treatment Period

Throughout the study protocol visits are noted by Days.

All subjects will be pretreated with enteric coated aspirin (81 mg QD for at least 7 days prior to randomization), and ticagrelor (180 mg loading dose, followed by 90 mg bid for a total of 5 doses of ticagrelor). The term "study drug" refers to PB2452/placebo.

Active: PB2452 is a ticagrelor-specific human monoclonal antibody fragment which binds to ticagrelor and TAM with high affinity, thereby reversing the antiplatelet effects of ticagrelor. It has no known off-target effects.

For this study, the investigational product will be supplied either as a lyophilized powder requiring reconstitution with sterile water for injection, or as a high-concentration liquid.

PB2452 18 g intravenous infusion will consist of 6 g infused over 10 minutes followed by a 6 g loading dose infused over 4 hours, then a maintenance dose of 6 g infused over the next 12 hours immediately following completion of the loading period for a total infusion time of approximately 16 hours and 10 minutes.

Note that if a subject is taking a moderate or strong CYP3A inhibitor, a 36 g alternative regimen of PB2452 will be administered consisting of 12 g infused over 10 minutes followed by a 12 g loading dose infused over 6 hours, then a maintenance dose of 12 g infused over the next 18 hours immediately following completion of the loading period for a total infusion time of approximately 24 hours and 10 minutes.

Placebo: 0.9% sodium chloride IV infusion, to be delivered as an infusion identical to the active drug regimens.

Ticagrelor: Ticagrelor 90-mg oral tablet (immediate release); administered as 180 mg (2×90 -mg tablet) loading dose plus 90 mg every 12 hours for 4 additional doses.

Aspirin: Enteric costed aspirin 81 mg oral tablet administered daily between Day -7 to the morning on Day 1, for a total of 8 tablets given prior to dosing with study medication.

Subjects may resume aspirin after discharge from the study on Day 3.

6.1.4 Safety Follow-up Period

All AEs must be reported in detail on the appropriate page of the eCRF from the time of consent through the date of the EOS Day 35 ± 3 . Adverse events must be followed until resolved or stable or judged by the Investigator that further follow-up is not required.

6.1.5 Unscheduled Visits

Unscheduled visits will be performed as necessary at the discretion of the Principal Investigator to follow-up on Adverse Events and safety issues. All details must be captured in source documents and eCRF as applicable.

6.1.6 End of Study

All subjects will return to the clinic at Day 35 ± 3 to complete the end of study (EOS) visit. The following procedures and assessments will be performed:

- Serum pregnancy test
- Physical examination, full, including height and weight
- Vital signs measured (SBP, DBP, RR, temperature and HR)
- 12-lead ECG
- Clinical laboratory tests including hematology, chemistry, coagulation, and urinalysis
- Blood sampling for PK: plasma PB2452, ticagrelor, and TAM PK
- Platelet biomarker sample collection (3.2% Na Citrate plasma tube)

Note: a single Qiagen PAXgene DNA tube per subject may be collected at any convenient sampling timepoint throughout the study

- Serum immunogenicity
- AEs/SAEs collected
- Concomitant medication(s)

6.1.7 Long-term Extension

There is no long-term extension. The trial concludes at the EOS (Day 35 ± 3) visit.

6.2 Discontinuation or Withdrawal

6.2.1 Individual Subjects

6.2.1.1 Treatment Discontinuation

A subject may withdraw consent and discontinue from the study at any time, for any reason, without prejudice to further treatment. Subject participation in the study may be stopped at any time at the discretion of the Investigator or at the request of the Sponsor, or if the study is terminated.

The Investigator may withdraw a subject from the study if the subject:

- Is non-compliant with the protocol
- Experiences a serious adverse event (SAE) or intolerable adverse event (AE) that, in the Investigator's opinion, requires withdrawal from the study
- Has laboratory safety assessments that reveal CS hematological or biochemical changes from baseline values
- During the course of the study and through the end of study develops symptoms or conditions listed in the exclusion criteria
- Requires a medication prohibited by the protocol
- Requests an early discontinuation for any reason

If a subject experiences a SAE or an intolerable adverse event (AE) that requires discontinuation in the opinion of the Investigator or as reported by the subject, then the Investigator may confer with the Sponsor regarding disposition of the subject. If a subject is discontinued from treatment because of an AE, the event will be followed until it is resolved or until the AE is stable in the opinion of the Investigator.

When a subject withdraws or is withdrawn from the study, the reason(s) for withdrawal will be recorded by the Investigator on the relevant page of the electronic case report form (eCRF). Whenever possible, any subject who withdraws from the study if willing, should continue to be followed according to the protocol. For example, if termination occurs earlier than planned (i.e., after a subject has received all or partial study drug infusion) all efforts should be made to ensure the remaining protocol visits are completed. If a subject refuses to return for the Follow-up visits, the Day 35 ± 3 visit procedures should be completed to the extent possible, and the site should try contacting the subject at least 3 times by letter, certified letter, phone call, email or other reasonable methods. All attempts to contact subjects and the final status of subjects who fail to complete final assessments will be documented in the source documents.

At the discretion of the Sponsor any subject who withdraws before completing the study, may potentially be replaced. Any replacement subject will be assigned to receive the same treatment as the subject he or she is replacing.

Clinical Study Protocol PB2452-PT-CL-0003-Phase 2b Version 2 dated 28May2021

6.2.1.1.1 Temporary Treatment Discontinuation

Though not expected, treatment may be discontinued temporarily at the discretion of the Investigator.

6.2.1.1.2 Permanent Discontinuation of Treatment

Treatment may be permanently discontinued at the discretion and based on clinical judgment of the Investigator. The Investigator is required to inform the Sponsor.

6.2.1.2 Withdrawal from Study

Subjects may withdraw from the study at any time at their own request or they may be withdrawn at any time at the discretion of the Investigator or Sponsor for safety, behavioral, or administrative reasons. If a subject does not return for a scheduled visit, every effort should be made to contact the subject. In any circumstance, every effort should be made to document subject outcome, if possible. The Investigator should inquire about the reason for withdrawal and request that the subject return for the EOS follow-up visit (complete procedures at final safety visit) and follow up with the subject regarding any unresolved adverse events.

If the subject withdraws from the study and also withdraws consent for disclosure of future information, no further evaluations should be performed, and no additional data should be collected. The Sponsor may retain and continue to use any data collected before such withdrawal of consent.

6.2.1.3 Replacement of Subjects

Subjects who withdraw from the study and who do not have adequate collection of safety, hemodynamic and pharmacokinetic samples for evaluation of safety, PK, and PD profiles may be replaced at the discretion of the Sponsor. Any replacement subject will be assigned to receive the same treatment as the subject he or she is replacing.

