3.1 Primary Objective and Endpoint

Primary Objective:

To demonstrate reversal of the antiplatelet effects of ticagrelor with intravenous PB2452 vs. placebo.

Primary Endpoint:

The primary study endpoint is the minimum % inhibition of platelet reactivity unit (PRU) assessed by VerifyNowTM PRUTestTM (VerifyNowTM, 2016) within 4 hours after the initiation of study drug. Percent inhibition of PRU is calculated as $100 * [(PRU_{bsl} - PRU_{trt})/PRU_{bsl}]$ where PRU_{bsl} refers to the PRU value measured before treatment with ticagrelor and PRU_{trt} refers to the PRU value measured before treatment with ticagrelor and PRU_{trt} refers to the PRU value measured posttreatment with the study drug.

Primary Endpoint Justification:

VerifyNowTM PRUTestTM is an effective and widely used clinical assay for assessment of ticagrelor's suppression of platelet function. It is a point-of-care assay that quantitatively assesses P2Y₁₂ dependent platelet aggregation. Degree of aggregation is reported on a PRU scale of 0-350. The lower limit of normal (LLN) platelet function is 180 PRU based on the assay's labeling.

Primary Endpoint Analysis:

Please refer to Section 9 of this protocol for further details.

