7.2.2 Randomization Strategy and Procedure

This study employs a simple randomization procedure without any stratification. The randomization will be employed via a Randomization & Trial Supply Management (RTSM) system.

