7.2.3 Extent and Maintenance of Blinding

The treatment assignment will not be known to Investigators, research staff, or study subjects. The following study procedures will be in place to ensure double-blind administration of study treatments.

This is a double-blind study. Neither the subjects nor the Investigator will be aware of the treatment assignment. Blinding will be maintained throughout the study by use of an opaque covering over the prepared dosage form to maintain blinding.

To maintain the blind, only designated pharmacy staff at the study site will have access to the randomization code and will prepare each dose for each subject. Except as noted above, all members of PhaseBio will remain blinded, except the unblinded Sponsor representative(s) who may be contacted in case of emergencies and if it is required to break the blind.

The study blind will be broken on completion of the clinical study and after the study database has been locked. If necessary (e.g., information required for enrolment in a subsequent study), a request may be submitted to the Sponsor to receive study treatment assignment for a subject.

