7.2.4.2 Unplanned or Unintentional Unblinding

During the study, the blind may be broken only in emergencies when knowledge of the subject's treatment group is necessary for further medical management. It is preferred (but not required) that the Investigator first contacts the medical monitor or PhaseBio study personnel to discuss options before unblinding the subject's treatment assignment

Unblinding of individual subjects may occur to ensure appropriate clinical management of a subject, for example if an SAE is considered by the Investigator as being causally related to study treatment OR in the event of a serious medical condition when knowledge of the study treatment is essential for the welfare of the subject as judged by the Investigator.

All unplanned, emergency unblinding will be considered as a protocol deviation. The date and reason for the unblinding must be fully documented.

A subject may continue in the study if that subject's treatment assignment is unblinded if it remains appropriate for them to do so and at the Sponsor's discretion.

PhaseBio's clinical or regulatory staff may request unblinding of thetreatment assignment for any subject with an SAE. If the SAE requires that an expedited regulatory report be sent to one

or more regulatory agencies, a copy of the report, identifying the subject's treatment assignment, may be sent to Investigators in accordance with local regulations.

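### Replacement subjects inherit the withdrawn subject's arm instead of being randomized, and concealment is at risk whenever that arm is known or can be inferred

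*Protocol*

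**What the plan says.** The same-arm sentence stands in three places: Protocol 6.2.1.1 (Treatment Discontinuation), Protocol 6.2.1.3 (Replacement of Subjects) and SAP 4.2 (Sample Size Justification). It reads: "Any replacement subject will be assigned to receive the same treatment as the subject he or she is replacing".

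The trigger differs between them. Protocol 6.2.1.3 and SAP 4.2 cover withdrawn subjects whose safety, hemodynamic and PK sampling was inadequate; they "PK, and PD profiles may be replaced at the discretion of the Sponsor". Protocol 6.2.1.1 is wider: "At the discretion of the Sponsor any subject who withdraws before completing the study, may potentially be replaced".

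Protocol 7.2.2 describes how arms are otherwise allocated: "This study employs a simple randomization procedure without any stratification". It is run through the RTSM. Protocol 9.2.2 and SAP 5 both define the mITT population by random assignment plus receipt of any study drug. Neither document says whether a subject with an inherited arm counts as randomly assigned, or how the RTSM links a replacement to the subject replaced.

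On masking, Protocol 7.2.3 says "The treatment assignment will not be known to Investigators, research staff, or study subjects", and that at the site "only designated pharmacy staff at the study site will have access to the randomization code".

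**The concern.** A replacement's arm is set by who withdrew and by a discretionary sponsor decision, both of which come after randomization. If those subjects enter the mITT population, the primary comparison is presented as fully randomized when part of it is not.

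The practical danger is selection. Someone who knows or suspects the withdrawn subject's arm also knows or suspects the replacement's arm before that person is dosed. Eligibility is still being confirmed on Day 1 before randomization (Protocol 6.1), so there is room to act on that knowledge, whether deliberately or not. What is at stake is the claim that the comparison rests on random allocation, and possibly a small bias in the primary estimate.

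**Working it through.** **1. The plan's own figure.** Inputs from SAP 4.2: 150 and 50 subjects, difference 15, SD 20, two-sided alpha 0.05, two-sample t-test. The standard error is 20 × √(1/150 + 1/50) = 3.27. The noncentrality is 15 / 3.27 = 4.59 on 198 degrees of freedom. Power is 99.55% from the noncentral t and 99.58% from the normal approximation. For the Wilcoxon test named in Protocol 9.3.1, with relative efficiency 3/π, it is 99.43%. The stated power of more than 99% reproduces.

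**2. How far arm sizes vary anyway.** Under simple 3:1 randomization of 200, the placebo count has SD √(200 × 0.25 × 0.75) = 6.1 and a central 95% range of 38 to 62. Power is 98.5% at 162 vs 38 and 99.8% at 138 vs 62. The design already tolerates larger shifts than a few randomized replacements would add.

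**3. Power if replacements are randomized.** The documents give no dropout or replacement rate, so r = 5, 10 and 20 are assumed. With withdrawals proportional to arm and k of the r replacements drawn to placebo (binomial, probability 0.25, 95% range), the arm sizes are 150 − 0.75r + (r − k) and 50 − 0.25r + k.

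| r | k | Active / placebo | Power |
|---|---|---|---|
| 5 | 0 to 3 | 151.25 / 48.75 to 148.25 / 51.75 | 99.5 to 99.6% |
| 10 | 0 to 5 | 152.5 / 47.5 to 147.5 / 52.5 | 99.4 to 99.6% |
| 20 | 2 to 9 | 153 / 47 to 146 / 54 | 99.4 to 99.7% |

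In the extreme case, where every withdrawal is from placebo and every replacement is drawn to active, power is 99.3% (155 vs 45), 98.8% (160 vs 40) and 96.5% (170 vs 30). With no replacement at all, dropout of 5, 10, 15 or 20% in both arms leaves 99.4, 99.1, 98.8 or 98.3%.

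**4. Possible bias under the present rule.** Suppose r replacements all fall in one arm and differ systematically by s points. With the arm held at its planned size, its mean moves by r × s / n. Both r and s are assumed.

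| r | s | Placebo mean (n = 50) | Active mean (n = 150) |
|---|---|---|---|
| 5 | 5 | 0.5 | 0.17 |
| 10 | 10 | 2.0 | 0.67 |
| 20 | 20 | 8.0 | 2.67 |

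The planned difference is 15 points.

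**5. Can the arm become known?** Three sets of provisions, read together, say that it can.

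- *Unblinding.* A serious adverse event is a listed ground for withdrawal (Protocol 6.2.1.1). Sponsor clinical or regulatory staff may ask for the assignment "for any subject with an SAE", and an expedited report showing it may go to investigators (Protocol 7.2.4.2). Protocol 7.2.4.1 also allows unblinding in a medical emergency. Both the party that decides on replacement and the party that enrols can then know the arm.
- *Inference.* Protocol 3.1 says of the primary assay: "It is a point-of-care assay that quantitatively assesses" platelet aggregation. Protocol 2.1.4 reports platelet activity back to about 100% of baseline, with onset at the first reading, 5 minutes in the later Phase 1 cohorts. Protocol 7.2.3 describes an opaque cover for the dosage form but no masking of PRU results.
- *No bar.* None of the three replacement passages excludes a subject whose assignment has been revealed.

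For a freshly randomized subject, the best guess (always PB2452) is right 75% of the time. For the replacement of an unblinded subject it is right 100% of the time. This measures predictability, not bias.

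**The case against.** A reader might infer that the rule breaks allocation concealment outright. The documents do not support that. Investigators, research staff and subjects are blinded, and the inherited arm was itself drawn at random. While it stays masked, it cannot be foreseen and is unrelated to the new subject's characteristics. Nothing says the enrolling site is told that a candidate is a replacement, or that the replacement comes from the same site. This part of the objection stands.

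A reader might also infer that the rule serves no purpose. That is too strong. It holds the arms near 150 and 50, and it recovers missing samples in the arm that lost them. Under a fresh 3:1 draw, a replacement for a PB2452 subject has a 25% chance of receiving placebo and then adds no PB2452 PK data. The benefit is real, but power does not depend on it.

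It can further be said that a subject whose PRU response was clearly seen probably has adequate samples, and so falls outside Protocol 6.2.1.3 and SAP 4.2. This holds only in part. PK and PD sampling runs to 48 hours, so early readings can exist where the full profile is inadequate, and the wider trigger in Protocol 6.2.1.1 has no sample condition.

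Finally, dosing is a single directly observed in-clinic infusion and the primary window closes at 4 hours, so few losses before that point are to be expected. This argues for a small effect, not for keeping the rule.

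**Conclusion.** The point holds in a limited form. Replacements are not independently randomized, which departs from Protocol 7.2.2 and leaves their place in a population defined by random assignment unsettled. Concealment is conditional: intact while the replaced subject's arm is masked, lost once it is revealed or inferred.

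The likely effect on the primary result is small, a shift of 2.0 points in the placebo mean or 0.67 in the active mean in the middle case above. It would become material only if replacements were many, concentrated in placebo and markedly different. All replacement counts and shifts are assumptions, because the documents give none. This is a design weakness worth correcting, not an error in a stated number.

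**What to change.** In Protocol 6.2.1.1, Protocol 6.2.1.3 and SAP 4.2, replace the same-arm sentence with: *Replacement subjects are randomized 3:1 through the RTSM using the next available assignment.* Changing only some of these would leave the documents contradicting themselves.

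Reconcile the replacement trigger in Protocol 6.2.1.1 with the narrower one in Protocol 6.2.1.3 and SAP 4.2.

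Confirm that replaced subjects who received any study drug stay in the mITT and Safety populations. This mostly restates Protocol 9.2.2 and SAP 5. It still needs saying because SAP 4.4 describes mITT as also requiring a post-dose PRU value, which could drop a dosed, withdrawn subject.

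If anyone has already been replaced under the present rule, add a sensitivity analysis of the primary endpoint without those replacements.

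The cost is one sentence in three places and an RTSM setting. Final arm sizes may shift by a few subjects, and some replacements for PB2452 subjects will be drawn to placebo.
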